10.1 EVALUATION DURING TREATMENT/INTERVENTION

Each cycle will consist of 21 days. All assessments, imaging and procedures will be performed within a window of $+\text{-} 4$ days (with the exception of the pharmacokinetic assessments). The following assessments will apply to all patients enrolled in both the Phase I and Phase II portions of the study.

Table 3.0 Study Assessments.

	Baseline Labs ¹	Safety Run-In for DS-3201b	Cycle 1			Cycle 2		Cycle 3+		EOT
		7 days prior to C1D1 (C1D-7)	Day 1	Day 8	Day 15	Day 1	Day 8	Day 1	Day 8	
Informed consent	X									
History, physical exam, (including vital signs and performance status)	X	X	X	X	X	X	X	X	X	X
Medication review (both prior and concomitant)	X	X	X	X	X	X	X	X	X	X
Adverse events monitoring (both serious and all others)	X	X	X	X	X	X	X	X	X	X
Serum or urine pregnancy test (for women of childbearing potential). Serum test only at screening.	X (serum)	X	X			X		X		
CBC with differential	X	X	X	X	X	X	X	X	X	X
Comprehensive metabolic panel ²	X	X	X	X	X	X	X	X	X	X
Urinalysis with microscopic analysis ³	X		X			X		X		X
EKG	X		X	X		X	X	X	X	X
Hepatitis B, Hepatitis C and HIV antibody testing	X (if not done prior)									
Coagulation profile including fibrinogen	X									
Lipid profile	X									
CT chest abdomen and pelvis with contrast ⁴	X							X ⁴		
Brain MRI with and without contrast ⁴	X							X ⁴		
Research bloods for PDX engrafting in [name] Lab (MSK)		X				X				X

main campus patients only) ⁵										
Research bloods for circulating tumor cell (CTC) analyses with EPIC Sciences ⁶	X	X	X	X	X	X	X	X		X
Research bloods for cfDNA banking at MSKCC ⁷	X	X	X	X	X	X	X	X		X
Tissue sample for study correlates (archival or fresh tissue) ⁸	X									
Tissue sample for study correlates (fresh biopsy only) ⁸								X		X ⁹
DS-3201b Administration (daily)		X	X	X	X	X	X	X	X	
Irinotecan administration (Days 1 and 8 only)			X	X		X	X	X	X	
PK assessment ¹⁰		X	X	X	X	X				

¹ All baseline testing needs to be obtained with 28 days of starting therapy. Exceptions include CBC, CMP, coagulation profile including fibrinogen, which must be obtained within 14 days.

² Includes electrolytes, BUN/creatinine, sodium, potassium, chloride, carbon dioxide, BUN/creatinine, calcium, glucose, AST, ALT, alkaline phosphatase, total bilirubin, direct bilirubin, albumin, total protein, magnesium, phosphorus, LDH.

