³ Urinalysis will include assessments of turbidity and color, pH, specific gravity, protein, ketones, bilirubin, occult blood, nitrite, glucose, and leukocyte esterase. Urine microscopic analysis will include erythrocytes, leukocytes, bacteria, casts, and crystals.

⁴ CT scans and brain MRIs will be obtained at the completion of every 2 cycles (approximately every six weeks).

⁵ CTCs for PDX engrafting will only be collected from samples from patient's treatment at MSKCC main campus. Due to feasibility barriers with transporting samples, no patient samples from MSKCC Regional Care Centers or from JHU will be collected for this purpose. Each sample will include two 10 cc EDTA tubes to be transported on ice.

⁶ CTCs for analysis by EPIC Sciences will be collected from all MSKCC sites and all JHU sites. Each sample will include one 10 cc Streck tube to be transported at room temperature.

⁷ CTCs for banking at MSKCC will be collected from all MSKCC sites and all JHU sites. Each sample will include one 10 cc Streck tube to be transported at room temperature.

⁸ Any fresh tissue biopsy will be performed ONLY if deemed medically safe by the institutional PI. There will be a window of +/- 4 days for the biopsy. The pre-treatment tissue sample can be archival if there is adequate tissue.

⁹ Post-progression tissue biopsy is OPTIONAL.

¹⁰ PK draws: There is a \pm 15-minute window for PK blood draws. PK assessments will be obtained in both Phase I and Phase II. Please see Table 4 for the complete PK schedule. Each PK blood draw will include 5 cc of blood collection.

Table 4.0 Pharmacokinetics (PK) Schedule for DS-3201b (Phase I and Phase II)

Cycle and Day	Time point						
7 days prior to C1D1	0.5-hour post-dose	1-hour post-dose	2-hour post-dose	4-hour post-dose	6-hour post-dose	8-hour post-dose	
Cycle 1 Day 1	Pre-dose	0.5-hour post-dose	1-hour post-dose	2-hour post-dose	4-hour post-dose	6-hour post-dose	8-hour post-dose
Cycle 1 Day 8	Pre-dose						
Cycle 1 Day 15	Pre-dose	0.5-hour post-dose	1-hour post-dose	2-hour post-dose	4-hour post-dose	6-hour post-dose	8-hour post-dose
Cycle 2 Day 1	Pre-dose						

Correlative Studies:

Studies Using Tumor Tissue:

We will obtain mandatory on-treatment core biopsies at Cycle 3 Day 1 +/- 4 days. The Cycle 3 Day 1 biopsy may be canceled if deemed medically unsafe (e.g., prior biopsy resulting in pneumothorax or other complication, bleeding diathesis, etc.) by the PI. The end of trial (EOT) biopsy will be optional.

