If DS-3201b needs to be held for any TEAEs as above, irinotecan should be held as well. When both study drugs are held for any particular visit due to TEAEs, counting of dose cycles will hold until their TEAEs have resolved or improved enough to meet protocol guidelines to restart treatment with both study drugs. If both drugs are held longer than 1 cycle (21 days), the treating physician must discuss eligibility for the patient to continue treatment on study with the study PI.

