11.6 Dose Delays and Modifications for Irinotecan

During Cycle 1 of Phase I dose-escalation, which includes the initial 7 days of safety run-in from Day -7 to Day 0, dose delays and dose modifications of irinotecan will not be used unless a DLT has been declared for purposes of determining the MTD. The outlined dose delays and modifications for both DS-3201b and irinotecan will be used in all patients in Phase I Cycle 1 if DLT has been declared, in all subsequent cycles of Phase I, and in all cycles of Phase II of this study. If toxicities are encountered, dosing adjustments and delays of DS-3201b and/or irinotecan will be made based on determination of the likely causative agent as outlined above

in Sections 11.2 and 11.3. Determination of the likely causative agent will be dependent on the treating physician if they feel that the toxicity is at least possibly related to either or both of the study drugs.

Usual clinical practice for dose delay and modification of irinotecan will be used, and dose adjustments will occur independent of DS-3201b dosing adjustments.

Patients should return to pre-treatment bowel function without requiring antidiarrhea medications for at least 24 hours before the next chemotherapy administration. A new cycle of therapy should not begin until the granulocyte count has recovered to $\geq 1500/\text{mm}^3$, and the platelet count has recovered to $\geq 100,000/\text{mm}^3$, and treatment-related diarrhea is fully resolved. Treatment should be delayed 1 to 2 weeks to allow for recovery from treatment-related toxicities. If the patient has not recovered after a 2-week delay, consideration should be given to discontinuing therapy.

If both study drugs are held for any particular visit due to TEAEs, then the patient would restart that same visit when their TEAEs have resolved or improved enough to meet protocol guidelines to restart treatment with either one or both study drugs.

If irinotecan needs to be held for any TEAEs as above, patients will have the option to continue DS-3201b as long as the TEAE is not also attributed to DS-3201b. However, counting of dose cycles will hold until their TEAEs have resolved or improved enough to meet protocol guidelines to restart treatment with irinotecan, regardless of whether patient continues DS-3201b. If both drugs are held longer than 1 cycle (21 days), the treating physician must discuss eligibility for the patient to continue treatment on study with the study PI.

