12.0 CRITERIA FOR THERAPEUTIC RESPONSE/OUTCOME ASSESSMENT

Determining the Safety, Tolerability, MTD and RP2D of DS-3201b in Combination with Irinotecan

The Common Terminology Criteria for Adverse Events (CTCAE) 5.0 will be used to determine all adverse events and dose-limiting toxicities.

Determining the Objective Response Rate (ORR) to Treatment with DS-3201b at the RP2D in Combination with Irinotecan

The Response Evaluation Criteria in Solid Tumors Group (RECIST v1.1) criteria will be used to evaluate the response to treatment.²⁹

Target Lesions

Change in disease will be assessed by repeat chest/abdomen/pelvis CTs at baseline and at every other cycle thereafter.

Complete Response (CR): Complete absence of all signs of disease without any new lesions or disease-related symptoms.

Partial Response (PR): A reduction of $\geq 30\%$ as compared to the baseline measurement.

Stable disease (SD): Neither sufficient shrinkage to qualify for PR nor sufficient increase to qualify for PD taking as references the smallest sum the longest diameter (LD) since the treatment started.

Progressive Disease (PD): An increase of $\geq 20\%$ over the nadir measurement is defined as progressive disease.

Non-Target Lesions

All other lesions (or sites of disease) not included in the "target lesions," including small lesions (longest diameter < 20 mm with conventional techniques or < 10 mm with spiral CT scan) and truly non-measurable lesions, should be identified as non-target lesions and recorded at baseline. Measurements are not required, and these lesions should be followed as defined below.

Lesions that are considered non-measurable include bone lesions, leptomeningeal disease, ascites, pleural/pericardial effusion, abdominal masses that are not confirmed and followed by imaging techniques, and cystic lesions.

Complete response: Disappearance of all non-target lesions.

Non-complete response/Non-progression: Persistence of one or more non-target lesions.

Progression: Appearance of one or more new lesions. Unequivocal progression of existing non-target lesions.

Evaluation of Best Overall Response

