The ORR is defined as the proportion of patients with CR, or PR at any reassessment after start based on RECIST v1.1 criterion. The time frame for evaluating the primary endpoint of ORR for this portion of the study will be 6 months from the date of Cycle 1 Day 1 for each patient. The ORR and corresponding exact 95% CI will be reported. Progression-free survival will be measured from the start of treatment until the documentation of disease progression or death due to any cause, whichever occurs first, and censored on the date of last tumor assessment. In addition, we will document absence of tumor progression for patients who are still alive prior to data cutoff, dropout, or the initiation of alternate anticancer treatment. Overall survival will be determined as the time from the start of DS-3201b treatment to death, and censored on the last follow-up date. PFS and OS will be evaluated using the Kaplan-Meier method. The duration of response (for those with CR or PR) and durable of stable disease while on treatment (for those with SD) will also be evaluated using the Kaplan-Meier method.

All recorded toxicity data and adverse events of DS-3201b will be listed and tabulated by system organ class, preferred term and treatment. Any significant vital signs and clinical laboratory test results will be listed and summarized. Any significant physical examination findings and clinical laboratory results will be listed.

As secondary objectives, we will explore downstream mechanistic biomarkers of DS-3201b including SLFN11 expression and H3k27me3 signature by descriptive and graphical summaries of assays performed on tissue samples obtained during the study. The Wilcoxon rank sum test will be used to assess SLFN11 expression by immunohistochemistry as a potential predictive biomarker of response to DS-3201b and to correlate with trimethylation of H3K27 as measured by immunohistochemistry in pretreatment, on-treatment and post-treatment tissue samples as well as in circulating tumor cells (CTCs). In addition, next-generation sequencing (NGS) will also be performed on pre-treatment, on-treatment and post-treatment tissue samples obtained from the study. This data will be analyzed using descriptive

and graphic summaries of the assays performed, including use of gene expression heat maps and advanced computational biostatistics with collaborators in the [name] laboratory.

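### Scans follow the cycle count, which stops during dose holds, so progression is documented somewhat later on average in patients with toxicity and some have fewer response assessments in the 6-month ORR window

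*Combined protocol and SAP*

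**What the plan says.** - **Imaging.** Table 3.0, footnote 4, in Section 10.1: "CT scans and brain MRIs will be obtained at the completion of every 2 cycles (approximately every six weeks". Section 12.0 repeats the cycle anchor: "Change in disease will be assessed by repeat chest/abdomen/pelvis CTs at baseline and at every other cycle thereafter".
- **Cycle length and window.** Section 10.1: "Each cycle will consist of 21 days". The same section adds "All assessments, imaging and procedures will be performed within a window of" plus or minus 4 days.
- **Cycle count when both drugs are held.** Section 11.5.4, which also requires irinotecan to be held whenever DS-3201b is: "counting of dose cycles will hold until their TEAEs have resolved or improved enough to meet protocol guidelines to restart treatment with both study drugs".
- **Cycle count when irinotecan alone is held.** Section 11.6 applies the same pause even if DS-3201b continues: "counting of dose cycles will hold until their TEAEs have resolved or improved enough to meet protocol guidelines to restart treatment with irinotecan".
- **Hold lengths.** Tables 5.0 and 6.0 allow DS-3201b interruptions of up to 28 days. Section 11.6 describes irinotecan delays of 1 to 2 weeks. Both sections call for discussion with the study PI once both drugs have been held for more than 21 days.
- **Endpoint clocks.** Section 14.0: "The time frame for evaluating the primary endpoint of ORR for this portion of the study will be 6 months", counted from each patient's C1D1; Section 12.0 uses the same 6 months. Section 14.0 dates a PFS event at documented progression or death.
- **Early stopping.** Section 13.1 still requires the first repeat CT, before the scheduled C3D1, from Phase II patients who finish the DLT period but stop before two cycles. It does not address patients who are on hold.

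**The concern.** The assessment clock pauses for toxicity while the endpoint clocks keep running. A patient whose treatment is held is scanned later than one who is not, and may be scanned fewer times inside the ORR window. The plus or minus 4-day window cannot absorb a hold of one to four weeks, and nothing in the documents keeps scans on the calendar during a hold.

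Holds are plausible. Sections 11.3.2 and 11.4.3 list cytopenias and diarrhea as common for both drugs. Table 8.0 omits irinotecan for, among other things, grade 3 neutropenia and grade 2 diarrhea.

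PFS is a Phase II secondary endpoint in a single-arm study, so no concurrent arm shares the delay. The average error favours the treatment and is concentrated in patients with toxicity. For ORR, Section 12.0 generally asks for confirmation of response, so the number of assessments in the window matters.

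**Working it through.** **1. The plan's own figures.** Two cycles are 2 × 21 = 42 days, which matches the stated six weeks only when there is no hold. The Simon design also reproduces. Stopping at 2 or fewer of 16 and requiring at least 9 of 31 gives, by exact binomial enumeration:
- type I error 0.047 at an ORR of 16%;
- power 0.801 at an ORR of 35%;
- probability of early stopping 0.516 at 16% (stated as 52%).

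This point does not affect those figures.

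**2. Scans in 26 weeks (182 days) from C1D1.** Scan dates are cumulative sums of (42 + hold) days.

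| Hold pattern | Scan days | Scans |
|---|---|---|
| None | 42, 84, 126, 168 | 4 |
| One 7-day hold, first block | 49, 91, 133, 175 | 4 |
| One 14-day hold, first block | 56, 98, 140, 182 | 4 (the last on the boundary) |
| One 21-day hold, first block | 63, 105, 147 | 3 |
| One 28-day hold, first block | 70, 112, 154 | 3 |
| 21-day hold in every block | 63, 126 | 2 |
| 28-day hold in every block | 70, 140 | 2 |

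If each block independently has a 40% chance of a 3- or 4-week hold (assumed), the schedule contains 4 scans with probability 0.6⁴ = 0.13 and 2 scans with probability 0.4³ = 0.064. Otherwise it contains 3 (about 0.81).

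**3. Mean delay in documented progression.** Assumptions: exponential progression times with rate λ, progression dated at the next scheduled scan, and each two-cycle block lasting L = 6 weeks, or 6 + h weeks with probability p. The documented time is the sum of all blocks begun before progression, so its mean is E[L] / (1 − φ), where φ = (1 − p)e^(−6λ) + p·e^(−(6+h)λ). With scans fixed every 6 weeks it is 6 / (1 − e^(−6λ)).

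For an assumed true median of 2.5 months (10.87 weeks), λ = 0.693/10.87 = 0.0638. The fixed schedule gives 6/(1 − 0.6821) = 18.87 weeks.

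| h (weeks) | p | E[L] | φ | Mean documented (weeks) | Delay (weeks) |
|---|---|---|---|---|---|
| 1.5 | 0.20 | 6.3 | 0.6697 | 19.07 | 0.20 |
| 1.5 | 0.40 | 6.6 | 0.6572 | 19.25 | 0.38 |
| 3 | 0.40 | 7.2 | 0.6346 | 19.70 | 0.83 |
| 4 | 0.40 | 7.6 | 0.6207 | 20.04 | 1.16 |

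The formula is not sensitive to the assumed median. From 1.5 to 6 months the four delays run 0.19–0.21, 0.36–0.40, 0.78–0.88 and 1.10–1.23 weeks. Simulation of 400,000 patients for the two longer holds, at medians from 1.5 to 3 months, agrees. If instead only 25% of patients are ever held, for 7 to 28 days, the overall mean rises by about 0.2 to 4 days (medians of 2 to 6 months).

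**4. The observed median.** Same simulation, holds in 40% of blocks:

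| True median (months) | Fixed 6-week scans (weeks) | 3-week holds | 4-week holds |
|---|---|---|---|
| 1.5 | 12 | 9 | 10 |
| 2.0 | 12 | 12 | 12 |
| 2.5 | 12 | 15 | 16 |
| 2.8 | 18 | 15 | 16 |
| 3.0 | 18 | 18 | 16 |

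The median has no stable direction, because documented progressions sit on scan dates and the median jumps between them.

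**5. ORR.** Later or fewer scans can only miss responses, so type I error cannot rise. As an illustration, if 5% or 10% of true responses were lost (assumed) at 35%, the detectable rate would be 0.3325 or 0.315, and power would fall from 0.80 to 0.74 or 0.67. The documents give no basis for choosing a loss.

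**The case against.** The strongest reply is that the practical effect is small. Section 11.6 describes irinotecan delays of only 1 to 2 weeks; 28 days is a ceiling for DS-3201b, and holding both drugs beyond 21 days prompts discussion of whether the patient continues. PFS is secondary and descriptive, with no test or threshold. Deaths are dated independently of scans, and symptomatic patients may be scanned early. All of this stands, and it limits the size of the point. It does not remove the mechanism.

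It can also be said that the six-week gloss in footnote 4 already implies a calendar. During a hold, however, the two halves of that footnote disagree, and the two Phase II sites could apply them differently. Either reading needs the same clarification.

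Four stronger readings are tempting, and the documents do not support them:
- **Median PFS is inflated by 3 to 4 weeks.** A reader could infer this from the 2.5-month row in step 4. At 2.8 months the shift reverses, and at 2.0 months it vanishes. The documents state no expected PFS.
- **Duration of response is lengthened.** Section 12.0 starts that clock when response is first recorded, so a late scan can delay the start as well as the end. The net direction is not established.
- **Held patients get half the scans.** That requires a hold of three weeks or more in every block, which is about 6% of schedules even under the 40% assumption.
- **The ORR test is compromised.** A first scan at week 10 is still well inside 6 months, and any loss of responses works against the treatment.

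**Conclusion.** The point holds as a modest, avoidable weakness in the assessment schedule. That scans slip with holds while the endpoint clocks do not follows directly from the current text. What follows by arithmetic alone is a first scan at week 9 or 10 instead of week 6, and 3 scans instead of 4 in 26 weeks, after one early 21- or 28-day hold.

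The later average documentation of progression, roughly 0.2 to 1.2 weeks across the scenarios shown, rests on assumed exponential times and assumed hold frequencies and lengths. Early unscheduled scans and exactly dated deaths would reduce it. No overall bias in PFS can be fixed from the documents, and no direction can be claimed for the observed median. For ORR the only risk is some loss of power, of unknown size. The Simon design and its error rates are unaffected.

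**What to change.** In Table 3.0, footnote 4, and in Section 12.0, state that tumour imaging is done every 6 weeks (plus or minus 4 days) by calendar from C1D1 until progression, regardless of dose holds or cycle count. Both places must change, because amending the footnote alone would leave Section 12.0 contradicting it. Reconcile the Section 13.1 reference to the CT before the scheduled C3D1 with the calendar date.

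This keeps the six-week interval that the protocol already states and changes no dosing rule. The cost is a short amendment, at most one or two additional scans in patients with long holds, and scans that no longer always coincide with a cycle visit.

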11.1 TOXICITIES/SIDE EFFECTS

NCI Common Terminology Criteria (CTCAE): This study will utilize the most recent version of the Common Terminology Criteria version for Adverse Event (CTCAE) reporting (currently 5.0). A copy of the CTCAE can be downloaded from <http://ctep.info.nih.gov>. All treatment areas have access to a copy of the CTCAE.

All toxicities will be graded according to the CTCAE version 5.0. The grade of toxicity should be that seen despite maximal medical management. Attempts will be made as best as possible to determine whether the toxicity is related to irinotecan, DS-3201b, or the combination. Given overlap of some of the toxicities between DS-3201b and irinotecan, any toxicity that results in a dose adjustment in DS-3201b will be attributed only to DS-3201b. Any toxicity that results in a dose adjustment in irinotecan only will be attributed only to irinotecan. Any toxicity that results in dose adjustments in both DS-3201b and irinotecan will be attributed to both DS-3201b and irinotecan. Attribution of each toxicity to either DS-3201b and/or irinotecan will be determined by the treating physician if it is felt that the toxicity is at least possibly related to either one or both of the study drugs.

11.2 1 Definition of Treatment Emergent Adverse Events (TEAEs)

Adverse event means any untoward medical occurrence associated with the use of a drug in humans, whether or not considered drug related.

Life-threatening adverse event or life-threatening suspected adverse reaction.

An adverse event or suspected adverse reaction is considered "life-threatening" if, in the view of either the investigator or sponsor, its occurrence places the patient or subject at immediate risk of death. It does not include an adverse event or suspected adverse reaction that, had it occurred in a more severe form, might have caused death.

Serious adverse event or serious suspected adverse reaction.

An adverse event or suspected adverse reaction is considered "serious" if, in the view of either the investigator or sponsor, it results in any of the following outcomes: Death, a life-threatening adverse event, inpatient hospitalization or prolongation of existing hospitalization, a persistent or significant incapacity or substantial disruption of the ability to conduct normal life functions, or a congenital anomaly/birth defect. Important medical events that may not result in death, be life-threatening, or require hospitalization may be considered serious when, based upon appropriate medical judgment, they may jeopardize the patient or subject and may require medical or surgical intervention to prevent one of the outcomes listed in this definition.

Suspected adverse reaction means any adverse event for which there is a reasonable possibility that the drug caused the adverse event. For the purposes of IND safety reporting, "reasonable possibility" means there is evidence to suggest a causal relationship between the drug and the adverse event. Suspected adverse reaction implies a lesser degree of certainty about causality than adverse reaction, which means any adverse event caused by a drug.

Unexpected adverse event or unexpected suspected adverse reaction.

An adverse event or suspected adverse reaction is considered "unexpected" if it is not listed in the investigator brochure or is not listed at the specificity or severity that has been observed; or, if an investigator brochure is not required or available, is not consistent with the risk information described in the general investigational plan or elsewhere in the current application, as amended. "Unexpected," as used in this definition, also refers to adverse events or suspected adverse reactions that are mentioned in the investigator brochure as occurring with a class of drugs or as anticipated from the pharmacological properties of the drug, but are not specifically mentioned as occurring with the particular drug under investigation.

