11.5.4 Dose Delays and Modifications for DS-3201b

During Cycle 1 of Phase I dose-escalation, which includes the initial 7 days of safety run-in from Day -7 to Day 0, dose delays and modifications for DS-3201b will not be used unless a DLT has been declared for purposes of determining the MTD. The outlined dose delays and modifications for both DS-3201b and irinotecan will be used in all patients in Phase I Cycle 1 if DLT has been declared, in all subsequent cycles of Phase I, and in all cycles of Phase II of this study. If toxicities are encountered, dosing adjustments and delays of DS-3201b and/or irinotecan will be made based on determination of the likely causative agent as outlined above in Sections 11.2 and 11.3. Determination of the likely causative agent will be dependent on the treating physician if they feel that the toxicity is at least possibly related to either or both of the study drugs.

Please refer to Table 2 in Section 9.0 for full details regarding the dose levels for DS-3201b. An abbreviated version of Table 2.0 is shown below for reference.

Dose Level	DS-3201b Dose
Level -1	50 mg once daily
Level 1(Starting Dose)	100 mg once daily
Level 2	150 mg once daily
Level 3	200 mg once daily
Level 4	250 mg once daily
Level 5	300 mg once daily

If dose level reduction below Level -1 is needed to manage toxicity due to DS-3201b, then study treatment with both DS-3201b and irinotecan will be permanently discontinued unless discussed with the study PI.

Table 5.0 Dose Delays and Modifications for Hematologic TEAEs

ADVERSE EVENT GRADE	DOSE MODIFICATION INSTRUCTIONS
≥Grade 4 neutropenia (<0.5 x 10 ⁹ /L per NCI CTCAE v5.0) lasting >7 days	
• Interrupt administration of study drug DS-3201b up to 28 days.• Resume the study drug DS-3201b at the dose before interruption if lasting ≤7 days at a reduced dose (by 1 dose level). If lasting >7 days once resolved to ≤Grade 2
OR	

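### Section 11.1 attributes toxicity by which drug's dose was adjusted: its rules overlap, have no stated rank against the physician's judgement, and can contradict that judgement

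*Combined protocol and SAP*

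**What the plan says.** Section 11.1 notes that the two drugs share toxicities and then gives four statements on attribution. They are lettered here for reference.

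- Rule A: "any toxicity that results in a dose adjustment in DS-3201b will be attributed only to DS-3201b".
- Rule B: "Any toxicity that results in a dose adjustment in irinotecan only will be attributed only to irinotecan".
- Rule C: "Any toxicity that results in dose adjustments in both DS-3201b and irinotecan will be attributed to both DS-3201b and irinotecan".
- Rule D: "Attribution of each toxicity to either DS-3201b and/or irinotecan will be determined by the treating physician", where the toxicity is felt to be at least possibly related to one or both drugs.

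No order of precedence is given.

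Section 11.5.4 governs DS-3201b dosing and says that "dosing adjustments and delays of DS-3201b and/or irinotecan will be made based on determination of the likely causative agent"; Section 11.6 repeats this for irinotecan. Both sections leave that determination to the treating physician. Section 11.5.4 ends with a linked hold: "If DS-3201b needs to be held for any TEAEs as above, irinotecan should be held as well". Section 11.6, by contrast, says of irinotecan that "dose adjustments will occur independent of DS-3201b dosing adjustments". When irinotecan is the drug held, "patients will have the option to continue DS-3201b as long as the TEAE is not also attributed to DS-3201b".

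Table 6.0 has DS-3201b interrupted for Grade 3 QTc prolongation, Grade 4 arrhythmia and other Grade 4 non-laboratory events whatever the cause. For each of these it then provides for the case where the event is judged not due to DS-3201b, and in that case it allows resumption one dose level lower.

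Section 14.0 plans a tabulation that covers all recorded toxicity data and adverse events of DS-3201b, by system organ class, preferred term and treatment.

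**The concern.** A dose action is a management decision. It can be precautionary, or taken before the cause is known, so it is a poor substitute for a causality judgement. Once it becomes the attribution rule, events can move from one drug to the other, or from neither drug to DS-3201b, without anyone having judged them so.

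The Phase II part runs at two institutions. Both could follow Section 11.1 to the letter and label the same event differently. What is at stake is any per-drug reading of the safety table, and its agreement with the causality that Section 17.3 requires in each SAE report. Section 11.2 defines a suspected adverse reaction by evidence of a causal relationship, not by what was done to the dose.

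**Working it through.** No arithmetic applies. The check sets the rules side by side.

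**Step 1: apply Rules A to C to each possible dose action.**

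| Dose adjusted | Rule A | Rule B | Rule C | Labels |
|---|---|---|---|---|
| DS-3201b only | DS-3201b only | – | – | 1 |
| Irinotecan only | – | irinotecan only | – | 1 |
| Both | DS-3201b only | – | both | 2, incompatible |
| Neither | – | – | – | 0 |

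The third row arises because Rule B carries a condition that only irinotecan was adjusted, while Rule A has no matching condition. Rule D applies to every row and is not ranked against the others.

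**Step 2: check that the third row can occur through dose reductions alone.** Take Grade 4 thrombocytopenia. Table 5.0 resumes DS-3201b one level lower. Table 8.0 treats thrombocytopenia like neutropenia, so Grade 4 lowers irinotecan by two levels. Neither row states a causality condition. If the physician considers both drugs possibly responsible and both rows are applied, both doses fall. Rule A then says DS-3201b only, while Rules C and D say both. Low platelets are on the common list for each drug in Section 11, so this is the kind of overlap that the rules were meant to handle.

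**Step 3: check the rules against an explicit causality judgement.** Take a Grade 4 non-laboratory event.

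- Table 6.0 interrupts DS-3201b whatever the cause.
- Suppose the event is judged not due to DS-3201b and the drug is resumed one level lower, as Table 6.0 allows.
- DS-3201b has been reduced because of the event, so Rule A labels it DS-3201b only.
- The stated judgement is that DS-3201b was not the cause.

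This conflict exists whether or not a hold is an adjustment, because the dose was actually reduced.

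**Step 4: consider the linked hold.** The plan does not define a dose adjustment.

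- If a hold counts, every DS-3201b reduction for toxicity in Tables 5.0 and 6.0 follows an interruption, and Section 11.5.4 then holds irinotecan too. The first row of the table in Step 1 is empty for these events. All of them fall in the third row, with two labels.
- If a hold does not count, an event managed by a hold and resumption at the same dose gets no label from Rules A to C. The conflicts in Steps 2 and 3 remain.

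Interruptions for CYP3A or P-gp inhibitors (Table 5.1) are outside this, since no toxicity is being attributed.

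**Step 5: see what uses the labels.** The DLT definitions count an event whichever drug is blamed, so MTD does not depend on the split. Whether an event reflects disease rather than drug is settled there by the physician with the study PI, not by dose action. The Phase II toxicity stopping rule uses the same definitions. ORR uses none of this. What remains is per-drug attribution and its tabulation under Section 14.0.

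**The case against.** A reader might infer more than the text supports, in two ways.

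- **That the plan is circular,** with attribution following dosing and dosing following attribution. The documents do not force this. Sections 11.5.4 and 11.6 rest the choice of causative agent on the treating physician, and they point to Sections 11.2 and 11.3 rather than to Rules A to C. A coherent chain is available: physician's judgement, then dose action, then a label that follows the action. On that reading a label cannot change the decision that produced it.
- **That every DS-3201b hold for toxicity gets two labels.** This is true only if an automatic irinotecan hold is a dose adjustment resulting from the toxicity. The term is undefined, and Sections 11.5.4 and 11.6 name adjustments and delays as separate things.

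Three further points are fair.

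- Rule A may simply lack the word that Rule B has. Adding it would remove the overlap in Step 1, but not the conflict in Step 3, where DS-3201b alone may be reduced for an event judged not due to it.
- Section 11.1 introduces the rules by reference to overlapping toxicities, so they may have been meant only for those. As written, however, Rule A covers any toxicity.
- The tabulation sentence in Section 14.0 can be read as already covering all recorded toxicity, and SAE reports and potential Hy's Law events already require a causality assessment. This limits the harm but leaves Section 11.1 inconsistent.

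**Conclusion.** The point holds as a defect of definition. Rules A and C give incompatible labels to any toxicity that adjusts both drugs, Rule D has no stated rank, and Rule A can overrule an explicit judgement that DS-3201b was not the cause. None of this depends on whether a hold is an adjustment. If it is, the double label extends to every toxicity-driven DS-3201b hold.

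The size is small. The documents do not allow a count of affected events, and none is claimed. The consequences stop at per-drug adverse event attribution and its table. Section 14.0 plans no test or comparison of per-drug toxicity, and no decision rule of the trial changes.

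**What to change.** 1. In Section 11.1, delete Rules A, B and C. Keep Rule D as the sole attribution rule, and say that the treating physician records a causality judgement for each drug separately and independently of any dose action.
2. In Section 14.0, state that the table of all recorded toxicity is all-causality for the combination, with relatedness to each drug as a supportive table.
3. The sponsor should reconcile the linked hold in Section 11.5.4 with the statement in Section 11.6 that irinotecan adjustments are independent of those for DS-3201b. Which clinical rule should stand is not a matter for this review.

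The cost is a wording amendment, with no change to sample size, endpoint or decision rule under items 1 and 2. The case report form is not among the documents. If it does not already hold a causality field per drug for every adverse event, those fields must be added. Events already labelled under Rules A to C would need a check against the physician's judgement where one was recorded.
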